### **7.2 Analysis Sets**

#### **7.2.1 Safety Population**

The safety population will include patients who have received at least 1 dose of study drug. Safety population will be used for all safety, efficacy, and immunogenicity analyses, unless otherwise specified.

[figure not shown]
## 7.2.2 PK Population

The PK population will include patients with sufficient dosing and PK data to reliably estimate PK parameters.

The PK population will be used for PK analyses.

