## 5.0 ANALYSIS ENDPOINTS

### 5.1 Phase 1 Primary Endpoints

[figure not shown]
- Adverse events (AEs), serious adverse events (SAEs), assessments of clinical laboratory values, and vital signs measurements
- Serum concentrations of brentuximab vedotin, total therapeutic antibody, and plasma concentrations of MMAE

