## 7.0 METHODS OF ANALYSIS AND PRESENTATION

### 7.1 General Principles

In general, descriptive statistics (number of observations, mean, standard deviation (StdDev), median, minimum, and maximum) will be used to summarize continuous variables. Frequencies and percentages will be used to summarize categorical variables. Time-to-event data will be analyzed using the Kaplan-Meier method and results will be summarized by the 25th, 50th (median), and 75th percentiles, if estimable, with associated 2-sided 95% confidence intervals, as well as the percentage of censored observations.

Unless otherwise specified, safety and efficacy data will be summarized in the following 7 groups: 1.4 mg/kg phase 1 only; 1.8 mg/kg phase 1 only; 1.8 mg/kg phase 1&2 HL only; 1.8 mg/kg phase 1&2 sALCL only; 1.8 mg/kg phase 1&2 sALCL in first relapse only; 1.8 mg/kg all patients; all patients. Pharmacokinetic analyses will be summarized by dose and treatment cycle.

The baseline value is defined as the value collected at the time closest to, but prior to, the start of study drug administration, unless otherwise specified. A windowing convention will be used to determine the analysis value for a given study visit for observed data analyses.

All available efficacy and safety data will be included in data listings and tabulations. Data that are potentially spurious or erroneous will be examined under the auspices of standard data management operating procedures. In general, there will be no imputation of missing data. For time-related endpoints, subjects who have no specified events will be censored as specified for each respective endpoint in Section 7.8. Imputation rules for missing dates of AEs and concomitant medications are detailed in Sections 7.1.3 and 7.1.4.

SAS Version 9.2 (or higher) will be used for all analyses.

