## 7.9 Pharmacokinetic/Pharmacodynamic Analysis

### 7.9.1 Pharmacokinetic Analysis

Serum concentrations of brentuximab vedotin (ADC) and total therapeutic antibody (TAb), and plasma concentrations of monomethyl auristatin E (MMAE) will be determined using validated assays.

Descriptive statistics (eg, number of patients, arithmetic mean, geometric mean, StdDev, median, percentage of coefficient of variation (%CV), minimum, and maximum) will be used to summarize serum ADC, serum TAb, and plasma MMAE concentrations at each time point in Cycles 1 and 8 at each dose level. The mean concentrations-time profiles of ADC, TAb, and MMAE will be plotted for cycles 1 and 8. The complete set of the same data (Cycles 1-16 or up to the cycle where  $N \geq 3$ ) will also be plotted for each dose level for ADC on a single plot. Similar plots will be provided for the TAb and the MMAE. Individual patient concentration data will be listed and plotted over time by cycle and by dose level.

Noncompartmental analysis for the determination of PK parameters such as  $t_{max}$ ,  $C_{max}$ ,  $AUC_{0-21}$  day,  $AUC_{0-\infty}$ ,  $t_{1/2}$ , CL, and  $V_{ss}$  will be performed as data permits for ADC and TAb. The PK parameters of  $t_{max}$ ,  $C_{max}$ ,  $AUC_{0-21}$  day,  $AUC_{0-\infty}$ , and  $t_{1/2}$  will be estimated for MMAE. These parameters will be summarized by dose level and cycle. The summary statistics will consist of N, mean, StdDev, %CV, median, min, max, and geometric mean.  $AUC_{0-21}$  day or  $AUC_{0-\infty}$  of ADC at 1.4 mg/kg will be scaled to 1.8 mg/kg (parameter to be scaled with multiplication of 1.29) for purposes of evaluating estimated exposures at the 1.8 mg/kg dose across the PK population. The individual CL of ADC and TAb will also be computed by normalizing for the baseline body weight and body surface area. Individual patient values of the parameters will be listed by cycle.

The 1.8 mg/kg and scaled 1.8 mg/kg  $AUC_{0-21}$  day or  $AUC_{0-\infty}$  of ADC will be plotted against age and/or body weight. More exploratory plots may be presented in the CSR as needed.

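### The only PK population requires reliably estimable parameters, but the PK endpoint is concentrations, so very sparsely sampled patients drop out of the concentration summaries

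*SAP*

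**What the plan says.** Section 7.2.2 sets one entry condition for PK: "The PK population will include patients with sufficient dosing and PK data to reliably estimate PK parameters". It then says: "The PK population will be used for PK analyses". No exception follows, whereas the safety population rule in 7.2.1 allows for other specifications.

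Section 5.1 gives the phase 1 primary PK endpoint as "Serum concentrations of brentuximab vedotin, total therapeutic antibody, and plasma concentrations of MMAE". Section 5.5 lists the same concentrations as a phase 2 secondary endpoint.

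Section 7.9.1 plans two kinds of analysis:

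- **Concentrations.** Descriptive statistics for both serum analytes and for "plasma MMAE concentrations at each time point in Cycles 1 and 8 at each dose level", together with mean profiles for those cycles and a multi-cycle plot for each analyte.
- **Parameters.** A noncompartmental analysis that "will be performed as data permits for ADC and TAb", a shorter parameter list for MMAE, and plots of ADC AUC against age and/or body weight.

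On individual data, 7.9.1 says: "Individual patient concentration data will be listed and plotted over time by cycle and by dose level". It names no population there.

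**The concern.** A summary of concentrations at a time point needs a valid sample, a known dose and a known sampling time. It does not need enough samples to estimate a clearance or an area under the curve. Section 7.2.2 nevertheless makes parameter estimation the condition of entry to both kinds of analysis. A patient can therefore have valid measurements of a phase 1 primary endpoint and be left out of its summary for a reason unrelated to those measurements.

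What is at stake is the number of patients behind the concentration tables and mean profiles. It matters most at the lower dose, where the cohort is very small.

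**Working it through.** The SAP states no figure for the number of patients expected to fall outside the PK population, so there is none to reproduce. The check is a reading of the text, followed by simple arithmetic on size.

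**Step 1. Does the entry condition fit each analysis?**

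| Analysis (SAP 7.9.1) | Needs an estimable parameter? | Set that applies (7.2.2) |
|---|---|---|
| Concentration statistics by time point | No | PK population |
| Mean concentration profiles | No | PK population |
| Noncompartmental parameter tables | Yes | PK population |
| ADC AUC against age or weight | Yes | PK population |
| Individual listings and individual plots | No | None named in 7.9.1 |

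The condition suits rows 3 and 4. It is stricter than rows 1 and 2 need, and those rows summarise the endpoint itself.

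**Step 2. Does another rule cover concentrations?** The safety population (7.2.1) serves safety, efficacy and immunogenicity. The general rule in 7.1, "All available efficacy and safety data will be included in data listings and tabulations", does not mention PK data. Section 7.9.1 names no other set for the concentration summaries. Nothing overrides 7.2.2.

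**Step 3. How much does one exclusion matter?** Section 7.1 summarises PK by dose and cycle, and 7.9.1 by dose level. Neither splits PK by phase.

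- 1.4 mg/kg: one phase 1 cohort of 3 to 6 patients (sections 4.4 and 6.0). Share of patients lost per exclusion = 1/n, so 1/6 = 17% and 1/3 = 33%.
- 1.8 mg/kg: at least 15 sALCL plus at least 15 HL patients, counting phase 1 patients treated at the recommended dose. That gives 15 + 15 = about 30, assuming the recommended dose is 1.8 mg/kg, as the groups in 7.1 imply. Share per exclusion = 1/30 = 3.3%.

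If the lost patient would have had a value at a given time point, the standard error of the mean there rises by √(n/(n−1)), taking the standard deviation as unchanged: √(3/2) = 1.22, √(6/5) = 1.10 and √(30/29) = 1.02.

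**Step 4. How likely is an exclusion at 1.4 mg/kg?** The SAP gives no rate. If a proportion p of patients has data too sparse for parameter estimation (an assumption), the chance of losing at least one patient is 1 − (1 − p)^n:

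| Assumed p | n = 3 | n = 6 |
|---|---|---|
| 5% | 0.143 | 0.265 |
| 10% | 0.271 | 0.469 |
| 20% | 0.488 | 0.738 |
| 30% | 0.657 | 0.882 |

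Any loss from a cohort of 3 also takes it below the minimum of 3 patients that 7.9.1 sets for the multi-cycle plots. These figures illustrate a range and do not predict the loss.

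**The case against.** The strongest reply is that 7.2.2 may exclude very few patients. It does not say which parameters must be estimable or how much data is sufficient, and 7.9.1 foresees patients for whom only some parameters can be computed. The PK analysis is also descriptive, and this document ties no test or decision rule to the concentration tables. All of this stands. It limits the likely loss, but it does not explain why entry to a concentration summary should depend on parameter estimation at all.

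A reader might infer more than the text supports in five ways:

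- **That a child with peak and trough samples but no usable terminal phase is necessarily excluded.** The listed parameters include tmax and Cmax, which need no terminal phase, so that child may qualify. Only very sparse data are clearly excluded.
- **That failing on one analyte removes the other two.** Section 7.2.2 does not require parameters for all three analytes. It is silent on the matter.
- **That the concentrations vanish from every PK output.** The individual listings and plots name no population and may still show them.
- **That one exclusion costs 17% to 33% at either dose.** This holds only at 1.4 mg/kg, because 1.8 mg/kg is pooled across phases. These are also shares of patients. A sparsely sampled patient contributes fewer values than a complete one, so the share of data lost is smaller.
- **That the youngest or lightest children are lost most often, which would bias the age and weight plots.** Nothing in the SAP supports that pattern. Those plots use AUC, which needs an estimable parameter, so a concentration set would not add anyone to them.

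**Conclusion.** The point holds as a mismatch between an analysis set and its endpoint. Section 7.2.2 applies a condition that suits parameter analyses to concentration summaries that do not need it, and no other rule in the SAP relieves this. Followed as written, it gives a worse summary of a phase 1 primary endpoint, so it is worth correcting.

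The effect is confined to patients whose data are too sparse for reliable parameter estimation, and to the concentration tables and mean profiles. Their number cannot be computed from the SAP. The effect could be material at 1.4 mg/kg and is small per patient at 1.8 mg/kg. The sizes rest on a cohort of 3 to 6 at the lower dose and about 30 pooled patients at the higher dose; more patients at the higher dose would make the share smaller. No claim of selective loss or bias is made.

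**What to change.** Divide section 7.2.2 into two sets:

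1. **PK concentration set:** treated patients with at least one evaluable postdose concentration of the analyte in question. Use it for concentration summaries, mean profiles and concentration plots.
2. **PK parameter set:** the current definition, used only for parameter tables and AUC plots, with a statement that it is applied by analyte and by cycle.

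Name the relevant set beside each output in 7.9.1, including the individual listings and plots, where none is named now.

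The cost is a few lines of SAP text and one extra population flag, with no additional data collection. N will vary by time point, but the number of patients is already among the statistics that 7.9.1 plans to print. If no patient proves too sparsely sampled, the concentration results do not change.

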## 7.2.3 CCI

CCI

## 7.2.4 Response-Evaluable Population

The response-evaluable population will include patients who receive at least 1 dose of study drug, have measurable disease at baseline, and have 1 postbaseline disease assessment.

The response-evaluable population will be used for analyses of disease response, time to response and duration of response.

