## 6.0 DETERMINATION OF SAMPLE SIZE

Approximately 42 evaluable patients will be enrolled in this study. In the phase 1 portion of the study, up to 12 patients with relapsed or refractory CD30+ malignancies will be enrolled in 2 planned dose cohorts (3-6 patients per cohort), according to the standard 3 + 3 dose escalation scheme.

Once the MTD and/or RP2D have been reached, patients will be enrolled by diagnosis into two phase 2 study arms: relapsed or refractory sALCL or relapsed or refractory HL. A sufficient number of patients will be enrolled in the phase 2 portion of the study to have at least 15 evaluable patients with sALCL (including patients treated at the RP2D during phase 1), of whom at least 10 patients are in first relapse, and at least 15 evaluable patients with HL (including patients treated at the RP2D during phase 1).

The sample size is not based on statistical consideration. Based on the exact binomial confidence interval calculation, 10 responses observed out of the 15 evaluable patients (overall response rate of 66.7%) will provide a 95% confidence interval of (38%, 88%).

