## 7.8 Efficacy Analysis

Response rates (OR, CR, PR), time to response, and duration of response will be conducted using the response-evaluable population. The other efficacy evaluations will be conducted using the safety population unless otherwise specified. All efficacy data will be summarized for the 7 groups listed in Section 7.1. If the sample size is too small to do a certain analysis in a group, no results will be presented for that group.

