### 7.8.1 Primary Efficacy Endpoints

There is no primary efficacy endpoint in phase 1. The primary endpoint in phase 2 is overall response rate (ORR) of patients who achieve CR or PR as determined by an independent review facility (IRF) using PET, CT, MRI, and clinical assessment according to IWG revised response criteria.

The primary efficacy endpoint of ORR per IRF, along with CR rate, and PR rate will be summarized with 2-sided 95% exact confidence intervals. Response rates (OR, CR, and PR) will be summarized using the response-evaluable population.

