### 7.8.2 Secondary Efficacy Endpoints

Besides response rates per IRF, response rates (ORR, CR, PR) per investigator assessments will also be summarized for all 7 groups listed in Section 7.1. Response rates will be summarized with 2-sided 95% exact confidence intervals.

The other secondary efficacy endpoints include time to progression (TTP), time to response, duration of response (DOR), event-free survival (EFS), progression-free survival (PFS), and overall survival (OS). TTP, DOR, EFS, and PFS will be estimated using independent review facility (IRF) assessment unless otherwise specified. Time to response and DOR will be

summarized using the response-evaluable population; TTP, EFS, PFS, and OS will be summarized using the safety population.

TTP is defined as the time from the first dose until the first subsequent documentation of objective tumor progression. TTP will be censored on the last radiological assessment of measured lesions documenting absence of PD for patients who do not have objective tumor progression.

Time to response is defined as the time from the first dose until the first documentation of objective tumor response (CR or PR). Time to response will be censored on the last radiological assessment of measured lesions documenting absence of CR or PR for patients who do not have a CR or PR.

Duration of response in subjects with response (CR or PR) is defined as the time from start of the first documentation of objective tumor response (CR or PR) to the first subsequent documentation of objective tumor progression or to death due to any cause, whichever comes first. Duration of response will be censored on the day following the date of the last radiological assessment of measured lesions documenting absence of PD for patients who do not have objective tumor progression and are still on study at the time of analysis, are given antitumor treatment other than the study treatment or stem cell transplant (SCT), or are removed from study prior to documentation of objective tumor progression.

EFS is defined as the time from the first dose until any cause of treatment failure: disease progression per IRF (including progression events during follow-up period), premature discontinuation of treatment for any reason (ie, not completing 16 cycles of treatment due to any reason), or death due to any cause, whichever occurs first. EFS will be censored on the last PFS assessment date if none of the above events occur during the study.

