PFS is defined as the time from the first dose until disease progression or death due to any cause, whichever occurs first. PFS will be censored on the day following the date of the last radiological assessment of measured lesions documenting absence of PD for patients who do not have objective tumor progression and are still on study at the time of analysis, are given antitumor treatment other than the study treatment or SCT, or are removed from study prior to documentation of objective tumor progression. Patients lacking an evaluation of tumor response after their first dose will have their event time censored at the day of first dose.

OS is defined as the time from the first dose until death due to any cause. In the absence of confirmation of death, survival time will be censored at the last date the patient is known to be alive. Patients lacking data beyond the day of first dose will have their survival time censored at the day of first dose.

TTP, time to response, DOR, EFS, PFS, and OS will be analyzed using the Kaplan-Meier method, the 25th, 50th (median), and 75th percentiles, if estimable, will be presented along with the associated 2-sided 95% confidence intervals. The results will also be presented in figures (Kaplan-Meier plots).

A waterfall plot may be used to compare PFS per investigator from the current study versus PFS achieved with the last therapy received prior to study entry.

A waterfall plot will be used to summarize the greatest percent reduction in target lesions for individual patients.

Efficacy data will also be listed by patient.

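### The phase 2 primary ORR omits treated patients with measurable disease but no postbaseline assessment, and no companion rate counting them as non-responders is planned

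*SAP*

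**What the plan says.** Section 7.2.1 sets a default: "Safety population will be used for all safety, efficacy, and immunogenicity analyses, unless otherwise specified". The response analyses are an explicit exception. Section 7.2.4 limits the response-evaluable population to patients with at least one dose who "have measurable disease at baseline, and have 1 postbaseline disease assessment". Section 7.8 states: "Response rates (OR, CR, PR), time to response, and duration of response will be conducted using the response-evaluable population". Section 7.8.1 repeats this for the primary endpoint: "Response rates (OR, CR, and PR) will be summarized using the response-evaluable population", with two-sided exact 95% confidence intervals.

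Section 7.1 says that missing data are in general not imputed. No section classes a treated but never-assessed patient as a non-responder.

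Section 7.8.2 adds investigator-assessed response rates, but Section 7.8 places response rates on the same population. Section 7.10.2 tabulates CR and PR by antibody status and disease type without naming a denominator; that is not an overall ORR.

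EFS and OS use the safety population (Section 7.8.2). EFS counts death, progression and "premature discontinuation of treatment for any reason" as failure. OS counts death from any cause.

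**The concern.** Having a postbaseline assessment is something that happens, or fails to happen, after treatment starts. Response evaluation begins after two 21-day cycles (Section 4.4), so a patient who dies or withdraws before any assessment has no documented CR or PR and also disappears from the denominator. EFS and OS can record that patient's death as an event, and EFS can also record the premature discontinuation. The primary ORR records nothing.

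Phase 2 has one primary endpoint, reported as an estimate with its interval. Arms are planned at 15 or more evaluable patients, and the sALCL arm carries a smaller subgroup ("of whom at least 10 patients are in first relapse") that is one of the 7 summary groups. At these sizes one patient visibly moves the estimate and both limits. The exact interval expresses sampling error only; it does not allow for selection into the denominator.

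**Working it through.** **Inputs.** From the SAP: 10 responses in 15 evaluable patients, 66.7%, 95% CI (38%, 88%) (Section 6.0); exact two-sided intervals (Section 7.8.1); at least 10 sALCL patients in first relapse (Section 6.0). Assumed: k, the number of treated patients with measurable disease and no postbaseline assessment, and every responder count other than 10/15.

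**Step 1: reproduce the plan's figure.** The Clopper-Pearson limits for x responders in n are the 2.5% quantile of Beta(x, n − x + 1) and the 97.5% quantile of Beta(x + 1, n − x). For 10/15 they are 38.4% and 88.2%, matching the stated (38%, 88%).

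**Step 2: direction.** Adding k patients as non-responders changes x/n to x/(n + k). The drop is

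x/n − x/(n + k) = (x/n) × k/(n + k),

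which is never negative. It is zero only if k = 0 or x = 0.

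**Step 3: size behind 10/15.**

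| k (assumed) | Rate | Exact 95% CI | Drop, points |
|---|---|---|---|
| 0 | 10/15 = 66.7% | 38.4% to 88.2% | 0 |
| 1 | 10/16 = 62.5% | 35.4% to 84.8% | 66.7 × 1/16 = 4.2 |
| 2 | 10/17 = 58.8% | 32.9% to 81.6% | 66.7 × 2/17 = 7.8 |
| 3 | 10/18 = 55.6% | 30.8% to 78.5% | 66.7 × 3/18 = 11.1 |

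**Step 4: dependence on the response rate.** With n = 15 and k = 1, the drop is 33.3 × 1/16 = 2.1 points at 5/15 and 93.3 × 1/16 = 5.8 points at 14/15.

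**Step 5: first-relapse sALCL group.** With 10 patients and an assumed 7 responders, 7/10 = 70.0% (34.8% to 93.3%). With k = 1 it is 7/11 = 63.6% (30.8% to 89.1%), and with k = 2 it is 7/12 = 58.3% (27.7% to 84.8%).

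**Step 6: scale.** The interval at 10/15 is 88.2 − 38.4 = 49.8 points wide. The shifts are small beside that, but they all go one way.

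**The case against.** A response-evaluable denominator is common in small phase 1/2 trials, and here it is disclosed. Much of the defence stands.

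- *No contradiction.* A reader might infer that Section 7.2.1 conflicts with Sections 7.8 and 7.8.1. It does not: the default yields where another population is specified, and those sections agree with 7.2.4.
- *Few patients, perhaps none.* A reader might infer that early progressors are dropped. The text does not support that. Any one disease assessment suffices, and Section 4.4 provides for an end-of-treatment evaluation and extra evaluations when clinically indicated. Only patients with no assessment of any kind are lost. Three behind 10/15 would mean 3 of 18 (17%).
- *No decision depends on it.* The SAP states no test, null rate or success threshold, and it plans no interim analysis. Section 7.3 reports the size of each population, and efficacy data and deaths are listed by patient, so a reader could rebuild the other rate.
- *PFS gives no contrast.* It is tempting to say that only the response analyses drop these patients, because for PFS "Patients lacking an evaluation of tumor response after their first dose will have their event time censored at the day of first dose". But a patient censored at time zero leaves the risk set before the first event and changes no step of the Kaplan-Meier curve. PFS retains them in name only. The contrast holds for EFS and OS.
- *Replacing the primary population is not called for.* Section 6.0 frames precision in evaluable patients, the protocol is not at hand, and the choice of primary set is a debatable trade-off. Sections 4.4 and 6.0 do not say that evaluable means the 7.2.4 set, but this is at most missing detail.

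What remains is that the plan offers no ORR free of this selection. Listings that let a reader derive one do not replace a prespecified estimate with its interval.

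**Conclusion.** The point holds as a gap in the planned reporting, not as an error in the primary analysis. As written, the exclusion can only leave the primary ORR unchanged or raise it relative to counting never-assessed patients as non-responders. This concerns the assessment requirement alone; nothing is claimed about the direction of the measurable-disease requirement.

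The size rests wholly on an assumed k: no effect if every such patient has an assessment, about 4 points for one patient behind 10/15, and about 11 for three. A reader might infer that the trial's ORR will be overstated by some such amount. The SAP supports the direction but gives no count, so no actual inflation can be asserted. The effect is on a descriptive estimate and its interval, not on type I error.

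**What to change.** Keep the response-evaluable ORR as primary. In Section 7.8.1, prespecify beside it a supportive analysis: ORR, CR and PR rates per IRF, with two-sided exact 95% CIs, in all patients who received study drug and had measurable disease at baseline, counting those with no postbaseline disease assessment as non-responders. Use the same grouping as Section 7.1 ("safety and efficacy data will be summarized in the following 7 groups"). Because Section 7.2 does not define this set, the new sentence should define it, and Section 7.8 should refer to it so that the two sections agree.

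The cost is a few lines of text and one extra set of response-rate tables, with no new patients or data. The companion ORR may be a few points lower, and it is conservative where a withdrawal has nothing to do with the disease. If no patient is unassessed, the two rates coincide and nothing is lost. Time to response and duration of response need no change: censoring a never-assessed patient at first dose would not alter the time-to-response curve, and duration of response uses responders only.
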